11.8 Subject Diary

The subject diary will be provided to the subject/parent/legal guardian/caregiver at Visit 1 and should be completed weekly on the day of study drug administration. The data captured within the subject diary includes:

- Date and time of administration
- Dose of study drug
- Person preparing and giving injection
- Location of injection on subject's body
- Assessment of subject pain using the Wong-Baker FACES Pain Rating Scale (see [Appendix 2](#))
- Assessment of local tolerability
- Changes to medications or subject's health

The subject diary should be reviewed by trial staff at every trial visit as part of concomitant medication review, adverse event reporting and study drug compliance.

11.9 Bone X-Ray

To confirm open epiphyses (bone age ≤ 14.0 years for females or ≤ 16.0 years for males), a bone age x-ray must be performed for subjects at Tanner stage 4 only. An x-ray performed within the past 52 weeks with a bone age delay of ≥ 6 months is acceptable. If not available, a bone age x-ray must be performed at Screening and read locally.

11.10 Laboratory Assessments

For subjects > 3 years old at Visit 1, the total blood volume collected throughout the trial will be no more than approximately 44mL.

For subjects ≤ 3 years old at Visit 1, the total blood volume collected throughout the trial will be no more than approximately 54mL.

Further details are provided in the trial manual.

11.10.1 Screening Laboratory Assessments

The following laboratory assessments will be performed on blood collected at Screening:

1. IGF-1 and IGFBP-3
2. Antibodies against hGH and PEG
 - These analyses may only be conducted after enrollment and are not required for eligibility verification. These data will be used to support evaluation of post-dose antibody detection.
 - If warranted, hGH and PEG serum levels may be analyzed for the interpretation of immunogenicity titers.
3. Hormone/glycemic status (TSH, FT4, FT3, morning cortisol, and HbA1c)
4. Chemistry
5. Hematology
6. Lipid panel
7. **For female subjects of child-bearing potential only:** hCG

Additionally, banked blood samples may be used for additional characterization of anti-drug antibody responses.

11.10.2 C_{max} Visit Laboratory Assessments

The following laboratory assessments will be performed on blood collected at the C_{max} Visit for subjects < 3 years old (at Visit 1):

1. hGH
2. IGF-1 and IGFBP-3
3. Hormone/glycemic status (TSH, FT4, FT3, morning cortisol, and HbA1c)

11.10.3 Visit 2 Laboratory Assessments

The following laboratory assessments will be performed on blood collected at Visit 2:

1. IGF-1 and IGFBP-3
2. **For subjects < 3 years old (at Visit 1) only:** mPEG
3. Antibodies against hGH and PEG
 - If warranted, TransCon hGH, hGH and PEG serum levels may be analyzed for the interpretation of immunogenicity titers.
4. Hormone/glycemic status (TSH, FT4, FT3, morning cortisol, and HbA1c)
5. Chemistry
6. Hematology
7. Lipid panel
8. **For female subjects of child-bearing potential only:** hCG

Additionally, banked blood samples may be used for additional characterization of anti-drug antibody responses.

11.10.4 Visit 3 Laboratory Assessments

The following laboratory assessments will be performed on blood collected at Visit 3:

1. IGF-1 and IGFBP-3
2. **For subjects < 3 years old (at Visit 1) only:** mPEG
3. Antibodies against hGH and PEG
 - If warranted, TransCon hGH, hGH and PEG serum levels may be analyzed for the interpretation of immunogenicity titers.
4. **For subjects \geq 9 years (at Visit 1) old only:** TMPD (N1,-N1,-N3-trimethyl-1,3-propane-diamine; a small molecular weight leaving group associated with the linker)
5. Hormone/glycemic status (TSH, FT4, FT3, morning cortisol, and HbA1c)
6. Chemistry
7. Hematology
8. Lipid panel
9. **For female subjects of child-bearing potential only:** hCG

Additionally, banked blood samples may be used for additional characterization of anti-drug antibody responses.

11.11 Local Tolerability Assessment

Local tolerability is defined as an injection site reaction deemed abnormal from those ordinarily observed in SC injections (including pain, intensity, or duration).

11.11.1 Local Tolerability Documentation

At Visit 1, assessment of local tolerability will be performed by trial staff using the Local Tolerability Scale (see [Appendix 1](#)) at the time of the first study drug injection and 15 minutes, 1 hour and 2 hour post-dose. At the same time, and as part of subject diary training, the subjects/parents/legal guardians/caregivers will document their assessment of local tolerability in the subject diary, within which injection site pain will be rated by the Wong-Baker FACES Pain Rating Scale (see [Appendix 2](#)).

Between visits, local tolerability will be evaluated and documented by the subject/parent/legal guardian/caregiver in the subject diary.

At Visit 2 and Visit 3, assessment of local tolerability will be performed by injection site examination by trial staff (documented as part of the limited physical exam), in conjunction with subject diary review.

11.11.2 Reporting Local Tolerability as an Adverse Event

For the purpose of this trial, injection site reactions should not be documented as AEs unless the reaction:

- Impacts the subject's ability to perform daily activities, or
- Requires medical therapy (not including prophylactic therapy)

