A phase 2 clinical trial in pediatric subjects with GHD has been conducted as a multicenter, randomized, open-label, active-controlled, parallel-group trial of 3 doses of TransCon hGH (ACP-001; 0.14, 0.21 and 0.30 mg hGH/kg/week) compared to daily hGH (Genotropin 0.21 mg hGH/kg/week divided into 7 equal daily doses) over 26 weeks. 55 subjects were randomized, of whom 53 received study drug (12 subjects in the 0.14 mg hGH/kg/week, 14 subjects in the 0.21 mg hGH/kg/week and 14 subjects in the 0.30 mg hGH/kg/week TransCon hGH cohorts and 13 subjects in the 0.21 mg hGH/kg/week Genotropin cohort). Mean annualized HV among the 3 dose levels administered weekly ranged from 11.9 cm for the 0.14 mg/kg/week dose to 12.9 cm for the 0.21 mg hGH/kg/week dose to 13.9 cm for the 0.30 mg hGH/kg/week dose, which were all comparable to 11.6 cm for the active comparator, daily injections of Genotropin at a 0.21 mg hGH/kg/week dose ([Figure 2](#)).

Figure 2
Annualized Height Velocity (Mean +SD) in 53 Subjects After 26 Weeks of TransCon hGH vs. Genotropin Treatment

cm = centimeter; kg = kilogram; mg =milligram

No reports of drug-related serious or unexpected AEs were observed. AEs were generally mild and observed at the same level and nature compared between the 3 TransCon hGH cohorts and the Genotropin cohort. Injection site reactions were generally mild and transient and were observed at a rate that was similar to the daily hGH control arm. There were no observations of injection site nodule formation or lipoatrophy. Low immunogenicity (a single subject with a low titer) was consistent with published data for daily hGH. This subject, treated with the lowest dose of TransCon hGH (0.14 mg hGH/kg/week), demonstrated an annualized HV of 19.0 cm/year compared to the cohort mean of 11.9 cm/year. No neutralizing antibodies were detected. Maximum and average hGH blood concentration were comparable between equivalent weekly doses of TransCon hGH and daily hGH.

A dose-proportional increase in IGF-1 levels into the normal range was observed following dosing of the 3 TransCon hGH dose levels. Consistent with expectations, transient point values of IGF-1 standard deviation score > +2.0 have been observed in a small number of subjects and primarily in the high-dose treatment arm (0.30 mg/kg/week).

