12. ADVERSE EVENTS, SERIOUS ADVERSE EVENTS, AND REPORTING

12.1 Adverse Events

12.1.1 Definition

An AE is defined as any untoward medical occurrence in a clinical investigation subject administered a pharmaceutical product and which does not necessarily have a causal relationship with the treatment. An AE can therefore be any unfavorable and unintended sign (including abnormal laboratory finding), symptom, or disease temporally associated with the use of a medicinal (investigational) product, whether or not related to that product. An AE can arise with any use (eg, in combination with another drug), route of administration, formulation, or dose, including an overdose.

Possible AEs associated with TransCon hGH are listed in the Investigator Brochure or the accompanying Reference Safety Information. The adverse reactions associated with commercially available daily hGH-containing products that may or may not be observed with use of TransCon hGH are:

- Sudden death in pediatric patients with Prader-Willi syndrome; risk factors include morbid obesity, history of upper airway obstruction or sleep apnea, and unidentified respiratory infection
- Intracranial tumors, particularly meningiomas, in teenagers/young adults treated with brain irradiation as children
- Injection site reactions/rashes (as well as rare, generalized hypersensitivity reactions)
- Skin atrophy and lipoatrophy

Note: Rotating the injection site (see [Section 9.3](#)) is expected to decrease the risk of skin atrophy or lipoatrophy.

- Headaches
- Glucose intolerance, including impaired glucose tolerance/impaired fasting glucose as well as overt diabetes mellitus
- Intracranial hypertension with papilledema, visual changes, headache, nausea, and/or vomiting
- Fluid retention manifested by edema, arthralgia, myalgia, nerve compression syndromes (including carpal tunnel syndrome/paresthesias)
- Hypothyroidism (central [secondary] hypothyroidism may first become clinically evident or worsen in patients with GHD during hGH treatment)
- Slipped capital femoral epiphysis (occurs more frequently in patients with endocrine disorders or in patients undergoing rapid growth)

Note: Any subject with the onset of a limp or complaints of hip or knee pain should be carefully evaluated for a slipped capital femoral epiphysis.

- Progression of pre-existing scoliosis due to rapid growth (hGH has not been shown to increase the occurrence of scoliosis)

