3.3. STUDY ENDPOINTS

3.3.1. Safety Endpoints

The safety endpoints as measured throughout the 26 weeks of weekly TransCon hGH treatment include the following:

- Incidence of AEs
- Local tolerability, as assessed by the subject/parents/legal guardians/caregivers and trial staff
- Incidence of antibodies against hGH, including neutralizing antibodies
- Incidence of antibodies against PEG
- Incidence of IGF-1 SDS >2.0, >3.0 with confirmation
- Parameters of HbA1c and lipids
- Hormone levels, including thyroid status and morning cortisol
- All other hematology and chemistry parameters
- Vital sign measurements

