8.1. ADVERSE EVENTS

AE is defined as any untoward medical occurrence in a clinical investigation subject administered a pharmaceutical product and which does not necessarily have a causal relationship with the treatment. An AE can therefore be any unfavorable and unintended sign (including abnormal laboratory finding), symptom, or disease temporally associated with the use of a medicinal (investigational) product, whether or not related to that product. An AE can arise with any use (eg, in combination with another drug), route of administration, formulation, or dose, including an overdose.

An AE is considered treatment emergent, ie, Treatment Emergent Adverse Event (TEAE), is any AE that was first occurred or worsened after the first study dose and before the end of study. If the AE has any missing start date, the rules stated in [Section 5.2](#) will be applied to determine if it is treatment-emergent.

A serious AE (SAE) is SAE is any untoward medical occurrence that:

- Results in death
- Is life-threatening
- Requires inpatient hospitalization or prolongation of an existing hospitalization
- Results in persistent or significant disability/incapacity
- Is a congenital anomaly/birth defect

Summaries of incidence rates (frequencies and percentages) of individual TEAEs by MedDRA SOC and preferred term will be prepared. Such summaries will be displayed for all TEAEs, TEAEs by maximum intensity, and TEAEs by strongest relationship to study drug. In addition, related TEAE, non-related TEAE, TEAE leading to study drug discontinuation, and serious TEAE, by SOC, the preferred term and TEAE by preferred term will be also summarized. Especially, related includes definite, probable and possible relationship. Not-related includes unlikely/remote and unrelated/not related.

Each subject will be counted only once within each preferred term. If a subject experience more than one TEAE within a preferred term, only the TEAE with the strongest relationship or the maximum intensity, as appropriate, will be included in the summaries of relationship and intensity.

Data listing of AEs, TEAE leading to study drug discontinuation, serious TEAE will also be provided.

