8.2. LOCAL TOLERABILITY

Local tolerability is defined as an injection site reaction deemed abnormal from those ordinarily observed in SC injections (including pain, intensity, or duration).

At Visit 1, assessment of local tolerability will be performed by trial staff using the Local Tolerability Scale at the time of the first study drug injection and 15 minutes, 1 hour and 2-hour post-dose. At the same time, and as part of subject diary training, the subjects/parents/legal guardians/caregivers will document their assessment of local tolerability in the subject diary, within which injection site pain will be rated by the Wong-Baker FACES Pain Rating Scale.

Between visits, local tolerability will be evaluated and documented by the subject/parent/legal guardian/caregiver in the subject diary.

At Visit 2 and Visit 3, assessment of local tolerability will be performed by injection site examination by trial staff local tolerability will be summarized based on the investigator's and subject/parents/legal guardians assessment of redness, bruising, swelling and pain.

Descriptive summary variables such as pain scale, redness, bruising and swelling will be produced for each assessment at each time point. A data listing of investigator's and subject/parents/legal guardian assessment will also be provided.

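### Injection site reactions that lead to stopping or changing drug need not be recorded as AEs, and the documents do not settle how skin atrophy, lipoatrophy and nodules are recorded or counted

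*Protocol*

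**What the plan says.** Safety and tolerability form the primary objective (Protocol 6.1). One safety endpoint is "Local tolerability, as assessed by the subject/parents/legal guardians/caregivers and trial staff" (SAP 3.3.1).

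Protocol 11.11.2 sets the threshold for moving a local reaction into the AE data: "injection site reactions should not be documented as AEs unless the reaction" meets one of two conditions. These are an effect on daily activities, or a need for therapy that is not prophylactic. No other condition is listed.

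Protocol 12.1.1 lists the known reactions to daily hGH. It gives "Skin atrophy and lipoatrophy" a separate entry from injection site reactions and rashes. The same section says that clinically significant new findings on physical examination are to be recorded as AEs. Footnote 16 of the schedule of events (Protocol 18.2) makes examination of the injection sites part of AE review. Nodules are not in the 12.1.1 list, but the account of the earlier pediatric trial in Protocol 5.3 reports on them: "There were no observations of injection site nodule formation or lipoatrophy".

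For local tolerability, SAP 8.2 plans that "Descriptive summary variables such as pain scale, redness, bruising and swelling will be produced for each assessment at each time point". For stopping drug, SAP 8.1 plans a summary of "TEAE leading to study drug discontinuation".

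**The concern.** An AE threshold for reactions that are also collected by diary and staff scale is a common and defensible choice. The difficulty is that this one has no exception for consequence. A reaction that makes a family skip doses, or stop, is a direct sign of poor tolerability. Yet it falls outside the AE data if the child was not treated for it and carried on with normal activities. The only table that links an event to stopping drug is built from AEs.

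The second difficulty is consistency. Two sites could see the same painless atrophic patch or nodule. One could record an AE under 12.1.1 and the other could leave it out under 11.11.2, each with text to support it. The count would then depend partly on which section the site followed.

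At stake is whether the report can state, per child, how often local intolerance led to stopping or changing drug, and how often atrophy or nodules appeared.

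**Working it through.** **1. The plan's own figure.** Protocol 14.2 and SAP 3.2 give at least 95% probability of observing an AE of 2% incidence with 150 subjects, and of 1% incidence with about 300. The formula is 1 − (1 − p)^n.
- n = 150, p = 0.02: 1 − 0.98^150 = 95.2%.
- n = 300, p = 0.01: 1 − 0.99^300 = 95.1%.

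Both reproduce. Both assume that every event is recorded as an AE.

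**2. A child who stops because of a local reaction.** Suppose the reaction is non-serious, is untreated and does not limit activity.
- AE data: not an AE under 11.11.2. The action-taken field of Protocol 12.1.3 is an attribute of an AE, so it is not completed for this reaction either.
- SAP 8.1 discontinuation table: counts TEAEs only, so the child is absent.
- SAP 6.1 disposition: gives reasons for leaving the trial. Protocol 8.2 urges children who stop drug to stay, so the child need not appear.
- SAP 8.7 exposure and compliance: shows a shorter duration, without a reason. The compliance rate need not show the stop. In SAP Table 3, duration is last dose date minus first dose date plus 7 days, and compliance is doses divided by weeks of duration. A child who stops after 6 weekly doses has 35 + 7 = 42 days, or 6 weeks, and compliance of 6/6 = 100%.
- SAP 8.2: shows the redness, bruising, swelling or pain score at that time point, not its consequence.

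The same path applies to a dose change. SAP 8.7 counts it once it meets the three-dose, 15% rule, but gives no reason. Missed doses lower compliance, again without a reason.

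**3. A painless atrophic patch or nodule found at Visit 2 or 3.**
- Toward exclusion: 11.11.2 covers injection site reactions for this trial, and such a lesion need not limit activity or need therapy.
- Toward inclusion: 12.1.1 lists atrophy and lipoatrophy apart from injection site reactions and makes clinically significant examination findings AEs. Footnote 16 puts site examination within AE review.
- No text ranks these provisions.
- If no AE is recorded, SAP 8.2 names no variable for the lesion and SAP 8.8 lists no physical examination summary. What remains is a listing, provided the finding was entered on the eCRF (SAP 5).

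**4. What under-recording does to the stated figure.** Let c be the share of true reactions recorded as AEs. The documents give no value for c, so this is an assumed range. For n = 150 and a true rate of 2%, the probability is 1 − (1 − 0.02c)^150.

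| c (assumed) | Chance of at least one recorded |
|---|---|
| 1.00 | 95.2% |
| 0.75 | 89.6% |
| 0.50 | 77.9% |
| 0.25 | 52.9% |
| 0.10 | 25.9% |

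The true rate needed for 95% is (1 − 0.05^(1/150))/c. This is 1.98% at c = 1, 3.95% at c = 0.5 and 7.9% at c = 0.25.

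**The case against.** The best defence is that local reactions are measured more closely here than AEs are. They have their own endpoint, a diary entry at each weekly dose, a staff scale at Visit 1 and site examinations at Visits 2 and 3. A threshold for AE recording avoids counting the same reaction twice. Screening and Visit 1 documentation of old daily hGH injection areas (Protocol 11.4) shows that new lesions are actively looked for. SAP 5 and 8.2 list the data. All of this stands, and it is why the threshold itself is not the complaint.

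A reader might infer that 11.11.2 certainly removes lipoatrophy and nodules from every table. The documents do not support that. The separate entry in 12.1.1, the examination-finding rule and footnote 16 all give a route to an AE record. The SAP 8.2 wording is also open-ended, and the Local Tolerability Scale in Appendix 1 is redacted, so a further item cannot be ruled out. What stands is an unresolved conflict and the lack of any named count.

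On stopping drug, the defence points to the Medical Monitor discussion in Protocol 12.2.1.3, the pre-approval in 9.6.2, and disposition reasons in SAP 6.1. The first two govern how a decision is made and create no AE record. The third covers children who leave the trial. The gap that remains is narrow: a non-serious, untreated, non-limiting reaction in a child who stops or changes drug and stays. It is real, because no text closes it.

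**Conclusion.** The point holds in two parts of unequal strength. The firmer part is that non-serious reactions leading to missed doses, dose change or stopping drug can go uncounted as such, because 11.11.2 lists two exceptions and consequence is not one of them. The weaker part is that atrophy, lipoatrophy and nodules have no settled recording rule and no named summary, so they may reach only the listings.

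The size cannot be stated from the documents. The figures for c below 1 are illustrations under an assumed recording share. A reader might go further and infer that a given number of affected children would be reported as none. No rate for such reactions on this product supports that. The only statement on atrophy or nodules is that none were observed in the earlier pediatric trial, which treated 53 children. Nor can it be said that the results would not be comparable with that trial, because its recording rule is not given.

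Serious reactions are not at issue, since Protocol 12.2 requires them to be reported. A generalized hypersensitivity reaction is not confined to the injection site, so 11.11.2 does not plainly exclude it.

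The conclusion assumes that no unseen eCRF page or manual closes the gap. The correction should be made because the data concerned bear on the primary objective and the change is small.

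**What to change.** The changes are to recording and tabulation only. No dosing or stopping rule is touched.

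1. In Protocol 11.11.2, add a third condition: an injection site reaction that leads to missed doses, a dose change or discontinuation of study drug is recorded as an AE. It then reaches the SAP 8.1 tables without further change.
2. Reconcile 11.11.2 with 12.1.1 and schedule footnote 16 by stating that skin atrophy, lipoatrophy and injection site nodules are recorded as AEs.
3. In SAP 8.2, add a per-subject count of atrophy or nodule, present or absent, from the Visit 2 and Visit 3 site examinations already performed.

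The cost is a small protocol and SAP edit and, if the eCRF has no field for it, one added item on an existing examination. AE counts for injection site reactions may rise slightly, and the report should say that this reflects the recording rule.

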12. ADVERSE EVENTS, SERIOUS ADVERSE EVENTS, AND REPORTING

12.1 Adverse Events

12.1.1 Definition

An AE is defined as any untoward medical occurrence in a clinical investigation subject administered a pharmaceutical product and which does not necessarily have a causal relationship with the treatment. An AE can therefore be any unfavorable and unintended sign (including abnormal laboratory finding), symptom, or disease temporally associated with the use of a medicinal (investigational) product, whether or not related to that product. An AE can arise with any use (eg, in combination with another drug), route of administration, formulation, or dose, including an overdose.

Possible AEs associated with TransCon hGH are listed in the Investigator Brochure or the accompanying Reference Safety Information. The adverse reactions associated with commercially available daily hGH-containing products that may or may not be observed with use of TransCon hGH are:

- Sudden death in pediatric patients with Prader-Willi syndrome; risk factors include morbid obesity, history of upper airway obstruction or sleep apnea, and unidentified respiratory infection
- Intracranial tumors, particularly meningiomas, in teenagers/young adults treated with brain irradiation as children
- Injection site reactions/rashes (as well as rare, generalized hypersensitivity reactions)
- Skin atrophy and lipoatrophy

Note: Rotating the injection site (see [Section 9.3](#)) is expected to decrease the risk of skin atrophy or lipoatrophy.

- Headaches
- Glucose intolerance, including impaired glucose tolerance/impaired fasting glucose as well as overt diabetes mellitus
- Intracranial hypertension with papilledema, visual changes, headache, nausea, and/or vomiting
- Fluid retention manifested by edema, arthralgia, myalgia, nerve compression syndromes (including carpal tunnel syndrome/paresthesias)
- Hypothyroidism (central [secondary] hypothyroidism may first become clinically evident or worsen in patients with GHD during hGH treatment)
- Slipped capital femoral epiphysis (occurs more frequently in patients with endocrine disorders or in patients undergoing rapid growth)

Note: Any subject with the onset of a limp or complaints of hip or knee pain should be carefully evaluated for a slipped capital femoral epiphysis.

- Progression of pre-existing scoliosis due to rapid growth (hGH has not been shown to increase the occurrence of scoliosis)

Note: Any subjects with a history of scoliosis should be monitored for progression of scoliosis.

- Pancreatitis - Cases of pancreatitis have been reported rarely in children and adults receiving hGH treatment, with some evidence supporting a greater risk in children compared with adults. Pancreatitis should be considered in any hGH-treated subject, especially a child, who develops persistent severe abdominal pain.

Clinically significant treatment-emergent physical examination or laboratory abnormalities and worsening pretreatment conditions should be recorded as AEs.

The Medical Monitor will review all AEs, including SAEs, on an ongoing basis. The key safety data will also be reviewed periodically by an ISC in accordance with its governing charter. Safety assessments will consist of monitoring and recording of all AEs, including SAEs, monitoring of hematology and chemistry parameters, physical examinations, vital sign assessments, and fundoscopies.

